BMS-986004 will be administered once every 2 weeks as an IV infusion for a total of 7 doses. Four (4) doses will be administered during the Response Phase over a 6 week treatment period. The remaining 3 doses will be administered during the Remission Phase of the study over a 6 week treatment period. Subjects will receive investigational product on Day 1/Week 0, Week 2, Week 4, Week 6, Week 8, Week 10 and Week 12, for a total of 7 doses.

Each dose cohort will enroll 10 new subjects, starting with the respective dose level at Day1/Week 0, regardless of the number of subjects joining a dose cohort because of intra-subject dose escalation.

A new cohort may be opened to treat subjects at a dose lower than 75 mg if at least 6 subjects treated at the 75 mg cohort achieve platelet Response (R) (platelet count $\geq 30,000/\text{mm}^3$ and at least 2-fold increase from the baseline count and absence of bleeding), at the end of response phase (Week 6). The new cohort would follow the same schedule as the other cohorts including intra-subject dose escalation.

The **long term extension (LTE)** period is optional and will include eligible subjects from either cohort 3 or cohort 4 who complete 12 weeks (85-days) of treatment and who achieve a response as defined by at least a doubling of platelets from Short Term Day 1 baseline and a platelet count of $\geq 35,000/\text{mm}^3$ and absence of bleeding and any significant AEs as assessed on D71 or if more recent platelet count is available, based on the most recent platelet count or on the average of the two consecutive most recent platelet counts, whichever is higher. If a subject has platelet counts close to a doubling of platelets and/or between 30,000-35,000 platelets/ mm^3 and absence of bleeding and any significant AEs as assessed on D71, the subject may be considered for the long term extension on a case by case basis, which will involve a review of data from the short term period and which will require approval by the Study Director.

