3.1.1 Intra-subject dose escalation

Intra-subject dose escalation could occur after the subject has completed the Response Phase of the study. The intra-subject dose escalation decision will be based on review of the safety information and platelet count after 4 weeks of treatment. The decision to escalate dose for the subject will be made after evaluating platelet count at Day 50, 7 days after the 4th dose of BMS-986004 has been administered. Subject will receive the next higher dose of BMS-986004 if clinically significant response has not been achieved based on measurement of platelet count on

the last two consecutive counts performed at Day 43 and Day 50, and a favorable safety profile is observed (see Table 3.1.1-1). Clinically significant response is defined as achieving platelet count $\geq 50,000/\text{mm}^3$ with an increase of at least $20,000/\text{mm}^3$ from baseline and absence of bleeding. Subject will then be dosed at the higher dose level for the remainder of the study (Remission Phase), receiving investigational product at that dose on Week 8, Week 10 and Week 12. Active treatment period with BMS-986004, regardless of the dose, may not exceed 12 weeks for any individual subject.

Table 3.1.1-1: Dose Adjustment after Response Phase

Platelet Count at Day 43 and Day 50 (7 days after the 4th dose) (X /mm³)	Action
< 50,000	Dose increase, as indicated by the next dose panel
$\geq 50,000$ with an increase of at least 20,000 from baseline	Dose remains constant on bi-weekly schedule

3.1.2 Dose frequency adjustment for responders exceeding 450,000/mm³ (for non-splenectomized subjects) and 600,000/mm³ (for splenectomized subjects) platelet count

For both the Short Term Study and the Long Term Extension plan, in the event that platelet count exceeds $450,000/\text{mm}^3$ for non-splenectomized subjects and $600,000/\text{mm}^3$ for subjects who underwent splenectomy, in the absence of recent (administered within two weeks) rescue medication, as indicated by the two consecutive platelet count measurements, dosing of the BMS-986004 should be stopped. Subject will remain in the study and platelet counts will be then assessed based on the normal study visit schedule. Dosing of BMS-986004 could be reinitiated only after discussion between Study Director and Investigator if clinically appropriate and dictated by the medical judgment and subject’s safety.

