If dose escalation is stopped due to any of these findings, additional cohorts may receive the same or lower doses of the investigational compound.

At the time of dose escalation, dose levels of new cohorts may be adjusted to lower doses if the accumulated safety data so dictates.

Adaptive dose selection may be performed to adjust some pre-selected doses, e.g., the third or/and fourth cohort doses, using accumulated efficacy and dose or exposure data. Models based on response rate, such as but not limited to (Bayesian) logistic regression, (Bayesian) EMax, may be utilized to predict a dose satisfying certain efficacy criteria, which might be different from the standard. If there are enough responding subjects with multiple platelet measurements, changes of platelet count may be directly modeled by dose and study day to facilitate dose prediction. The selected dose for a cohort should not exceed the originally planned dose for that cohort, i.e., selected dose for cohort C should not be larger than 675mg and it should be at most 1500 mg for cohort D.

The study design schematic is presented in [Figure 3.1.3-1](#).

Figure 3.1.3-1: Study Design Schematic: Short-term period

*Will not apply to subjects entering LTE

Figure 3.1.3-2: Study Design Schematic: Short-term period

Intra-Subject Dose Escalation

[figure not shown]
[figure not shown]

Figure 3.1.3-3: Study Design Schematic: Long term extension period

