3.1.5 Long Term Extension

The long term extension (LTE) period is optional and will include eligible subjects who have completed Day 85 (12-weeks of treatment) and who have consented to participate. Eligible subjects [platelet count $\geq 35,000/\text{mm}^3$ with at least a doubling of platelets from short-term baseline, or patients approved by the Study Director on a case by case basis who are close to a two-fold increase from short term baseline and/or have 30,000-35,000 $/\text{mm}^3$ platelets and absence of bleeding and any significant AEs as assessed on D71 or if more recent platelet count is available, based on the most recent platelet count or on the average of the two consecutive most recent platelet counts, whichever is higher], will receive a 1500 mg dose every other week for 24 weeks. Subjects who complete 24 weeks LTE will receive a taper regimen consisting of 1500mg dose on Day 190 and a final dose on Day 218 before entering the 24 week follow-up period (no treatment).

A separate informed consent must be signed by the patients to enter the LTE period.

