Physical Measurements	X	X*		X	X (On D248 and 398 only)	Weight only. *LTE D85 only
Vital Signs	X	X	X	X	X	Includes body temperature, respiratory rate, seated blood pressure and heart rate. Blood pressure and heart rate should be measured after the subject has been seated quietly for at least 5 minutes.
Electrocardiogram (ECGs)	X	X*		X		ECGs should be recorded after the subject has been supine for at least 5 minutes. *On Day 71 only.
Laboratory Tests	X	X	X	X	X	Includes blood and urine samples. Platelet count

Table 5.1-3: Long term Extension Procedural Outline (IM140103)						
Procedure / Visit Day (± 3 days is allowed for all visits, including LTE Day 1)	LTE D1^a	Every-other week Visits (Q2W) LTE D15, 29, 43, 57, 71, 85, 99, 113, 127, 141, 155, 169 (±3 days)	Taper Period Visit 1 LTE D190 (±3 days)	Taper Period Visit 2 LTE 218 (±3 days)	Monthly Follow-up Period LTE D248, 278, 308, 338, 368, 398 (±3 days)	Notes
						included in this test. (Hematology, Serum Chemistry, Urinalysis)
Pregnancy Test	X	X*	X	X	X	For women only (urine or serum) must be negative to continue dosing. *On LTE D29, D57, D85, D113, D141, D169 only
Adverse Event Reporting						
Monitor for Non-Serious Adverse Events	X	X	X	X	X	
Monitor for Serious Adverse Events	X	X	X	X	X*	*All SAEs must be collected within 3 months of discontinuation of dosing
PK & Immunogenicity Assessments						
PK Sampling	X	X	X	X	X*	*On LTE D248, D278, D308 only
Immunogenicity Sampling	X	X	X	X	X*	*On LTE D248, D278, D308 only

Table 5.1-3: Long term Extension Procedural Outline (IM140103)						
Procedure / Visit Day (± 3 days is allowed for all visits, including LTE Day 1)	LTE D1^a	Every-other week Visits (Q2W) LTE D15, 29, 43, 57, 71, 85, 99, 113, 127, 141, 155, 169 (±3 days)	Taper Period Visit 1 LTE D190 (±3 days)	Taper Period Visit 2 LTE 218 (±3 days)	Monthly Follow-up Period LTE D248, 278, 308, 338, 368, 398 (±3 days)	Notes
Biomarker Assessments						
Plasma Soluble Free CD40L Level		X	X	X		
Plasma Soluble Total CD40L Level		X	X	X		
Plasma Collection		X	X	X		
Clinical Drug Supplies						
Contact IVRS	X	X	X	X		
Study drug administration (1500 mg)	X	X	X	X		
Report to Study Site	X	X	X	X	X	(+/- 3 days visit window for all visits)

^a Study procedures performed on Day 85 of the short term period will be used as the starting point for LTE Day 1 procedures. They do not need to be performed twice. Patient in LTE, the Day 85 of the short term period and Day 1 of the LTE study dose are the same.

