8.2 Populations for Analyses

- All Enrolled Subjects: All subjects who sign an informed consent form.
- All Treated Subjects: All subjects who receive at least one dose of study medication, either BMS-986004 or placebo.
- Pharmacokinetic Subjects: All subjects who receive at least one dose of BMS-986004 and have available serum concentration data.

Biomarker Subjects: All treated subjects for whom pharmacodynamic measurements are available at both Short Term Day 1 baseline and at least one other time after treatment

LTE:

- LTE Analysis Population: All subjects who have received at least one dose of LTE medication of 1500 mg.

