7.7 Pharmacokinetics

PK sampling date and time are shown below in [Table 7.7-1](#) for convenience. On day 57, non-responders in each treatment group other than the 1500mg group will be dose-escalated to the starting dose of the next higher treatment group.

The Pharmacokinetic (PK) population will be used for all listings. Evaluable PK population will be used for summaries. PK parameters and C_{trough} will be summarized for each group decided by current dose, and dose proportionality analysis will be provided by excluding subjects who have dose escalation on day 57.

Table 7.7-1: PK Sample Study Day and Time

study day	dosing	PK Sampling
1	#1, at starting dose	0h, 2h, 24h, 72h, 168h
15	#2, at starting dose	0h
29	#3, at starting dose	0h
43	#4, at starting dose	0h, 168h
57	#5, Responder: at starting dose Non-Responder: at titration dose	0h, 2h
71	#6, at the same dose as Day 57	0h, 2h, 24h, 96h, 168h
85	#7, at the same dose as Day 57	0h, 336h, 672h

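### A cohort 3 subject held at 675 mg who enters the LTE has two doses specified for the Day 85 infusion, and the 12-week treatment limit in Section 3.1.1 contradicts the LTE

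*Protocol*

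**What the plan says.** **Short-term dosing.** Protocol Section 3.1 schedules the last three infusions at "Week 8, Week 10 and Week 12, for a total of 7 doses", and Table 5.1-2 ticks study drug administration at Day 85. For a subject who meets the clinically significant response rule at Days 43 and 50, Table 3.1.1-1 states: "Dose remains constant on bi-weekly schedule". SAP Table 7.7-1 describes the Day 85 infusion as number "7, at the same dose as Day 57".

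**LTE dosing.** The LTE is open to eligible subjects from cohorts 3 and 4. Under Section 3.1.5 they "will receive a 1500 mg dose every other week for 24 weeks". Table 4-2 lists 1500 mg as the only LTE dose, and the drug administration row of Table 5.1-3 is labelled 1500 mg and ticked at LTE Day 1. Footnote a to that table says: "Patient in LTE, the Day 85 of the short term period and Day 1 of the LTE study dose are the same".

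**Adjustment of panel doses.** Section 3.1.3 allows escalation to be put on hold. It says that "dose levels of new cohorts may be adjusted to lower doses if the accumulated safety data so dictates", and it caps cohorts C and D (the third and fourth panels) at 675 mg and 1500 mg without requiring those doses.

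**Length of treatment.** Section 3.1.1 states: "Active treatment period with BMS-986004, regardless of the dose, may not exceed 12 weeks for any individual subject".

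**LTE analysis set.** Section 8.2 defines it as "All subjects who have received at least one dose of LTE medication of 1500 mg".

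**The concern.** A site treating a cohort 3 responder held at 675 mg who has consented to the LTE cannot follow both instructions on Day 85. Different sites could resolve this differently, so the dose given would depend on which page was consulted.

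The reporting suffers too. Protocol Section 5.3 summarises treatment-emergent events through Day 85 by dose cohort. SAP Section 7.6 counts events to 35 days after the last dose for subjects off treatment. Neither says whether, in an LTE entrant, an event after the Day 85 infusion belongs to the short-term period or to the LTE. Safety is the primary objective of both periods.

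The 12-week sentence is a second contradiction: read as written, it rules out every LTE dose after Day 85.

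**Working it through.** **1. Dose calendar.**
- Short-term doses (Section 3.1, Table 5.1-2): Days 1, 15, 29, 43, 57, 71 and 85, so 7.
- LTE doses (Table 5.1-3): LTE Days 1, 15, 29, …, 169, so 13, plus taper doses on LTE Days 190 and 218, so 15 in all.
- Check against the protocol's own durations at the end of Section 3.1.4: (169 − 1)/7 = 24 weeks of dosing and (218 − 169)/7 = 7 weeks of taper. Both are reproduced.
- Footnote a sets LTE Day 1 = study Day 85, so study day = LTE day + 84.
- Distinct infusions: 7 + 15 − 1 = 21. Exactly one of them, Day 85, appears in both schedules.

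**2. The two specifications for Day 85, for a cohort 3 subject held at the planned dose.**

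| Source | Dose | Rate over 120 min |
|---|---|---|
| Section 3.1.1, Table 3.1.1-1; SAP Table 7.7-1 | 675 mg | 675/120 = 5.625 mg/min |
| Table 5.1-3 at LTE Day 1; Section 3.1.5; Table 4-2 | 1500 mg | 1500/120 = 12.5 mg/min |

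The rates agree with Tables 4-1 and 4-2. The ratio is 1500/675 = 2.22. Whether footnote a means one dosing occasion or one dose level, the conflict stands: on the first reading a single infusion has two doses, and on the second the statement is untrue for this subject.

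**3. Who is not affected.** A cohort 4 subject on 1500 mg, or a cohort 3 subject escalated to 1500 mg at Day 57, has the same dose under both schedules. If cohort D were set below 1500 mg, both groups would also have a Day 85 dose different from the LTE dose.

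**4. Length of treatment.** Day 1 to Day 85 is 84 days, or 12 weeks. The last LTE dose is at 218 + 84 = study Day 302, which is 301 days, or 43 weeks, after the first dose.

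**5. Number of subjects held at 675 mg.** The documents give no rate for the Day 43/50 rule (a count of at least 50,000/mm³, a rise of at least 20,000/mm³ and no bleeding). Assuming their general response rates approximate it:
- SAP Section 7.7.3, 20% to 50% for 75 to 675 mg: 10 × 0.20 = 2 to 10 × 0.50 = 5.
- Protocol Appendix 2, 0.55 at 675 mg: 10 × 0.55 = 5.5.

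Fewer would face the conflict, because the LTE is optional and has its own platelet criterion. For example, a rise from 28,000 to 50,000/mm³ meets the Day 43/50 platelet thresholds (+22,000) but is only 50/28 = 1.79-fold, short of the doubling needed for standard LTE entry.

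**6. Share of LTE entrants whose dose would rise at entry.** Assume also that the same rates approximate LTE eligibility, that all eligible subjects enter, that the cohort 4 rate is 0.70 and that the response rate after titration is 0.33 (both from Appendix 2).
- At 0.55: 5.5 held; 10 × 0.45 × 0.33 = 1.5 escalated; 7 in cohort 4. Share = 5.5/14.0 = 39%.
- At 0.20: 2 held; 10 × 0.80 × 0.33 = 2.6 escalated; 7 in cohort 4. Share = 2/11.6 = 17%.
- If no titrated subject responds: 2/9 = 22% to 5.5/12.5 = 44%.

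**The case against.** **The SAP may simply be older than the LTE.** Its Section 2.4 covers amendments through Amendment 02, and it contains no LTE analysis. This is fair, but Section 3.1.1 and Table 5.1-3 conflict within the protocol alone.

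**A clarification may sit in text that cannot be read.** Section 8.4.9, on exploratory LTE analyses, is redacted and the LTE schematic is not shown. This limits the finding to the readable text. It also means that the absence of an LTE analysis by prior dose cannot be asserted.

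**The 12-week sentence is short-term wording.** It directly follows the Week 8, 10 and 12 doses, and the LTE is a separate period with its own consent. That is probably what was meant, so a reader should not infer that the LTE breaches a safety limit. The sentence is nonetheless unscoped and names any individual subject.

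**A reader might infer that the overlap leaves the LTE unable to separate maintained response from the effect of a dose increase.** The documents do not support this. That confounding comes from the fixed 1500 mg LTE dose and would persist from LTE Day 15 whatever was given on Day 85. It touches only subjects whose dose rises at entry; those already on 1500 mg continue unchanged. The analysis is descriptive (Section 8.4.8), the endpoint counts achieved and maintained responses together (Section 8.3.4.1), and maintenance at an unchanged dose is not a stated objective.

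**A reader might also infer that LTE subjects will receive a dose the escalation rules have not cleared.** That is a contingency. A hold triggers review of all safety data across the study, and a data monitoring committee reviews safety. What stands is that Section 3.1.5 does not say what happens to the LTE dose if Section 3.1.3 leads to a hold or a lower cohort D dose.

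**The dose actually given will be recorded.** This is true, and since the two schedules share one infusion, counting six or seven short-term doses is only labelling. The planned dose and the period to which later events belong remain unspecified.

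**Conclusion.** The contradiction is real and must be fixed before a held cohort 3 subject enters the LTE. For that subject the readable protocol specifies two doses for one infusion, 675 mg and 1500 mg at the planned panel doses, and does not choose between them. About 2 to 5.5 of 10 cohort 3 subjects would be held at 675 mg, on the assumption that the documents' general response rates approximate the Day 43/50 rule. Fewer would face the conflict after LTE eligibility and consent. It would reach cohort 4 only if cohort D were set below 1500 mg.

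The 12-week sentence is a separate contradiction, with dosing planned to about study Day 302, and is most likely a matter of scope. The finding does not extend to the validity of the LTE as a whole. This review takes no position on which dose is right.

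**What to change.** - Reconcile Section 3.1.1 with Table 3.1.1-1, Section 3.1.5, Table 5.1-3 with footnote a, and SAP Table 7.7-1, so that one dose is specified for Day 85 in an LTE entrant.
- Assign that infusion, and the adverse events after it, to one period, and carry this into Protocol Section 5.3 and SAP Section 7.6.
- Reconcile the 12-week sentence in Section 3.1.1 with the LTE.
- Reconcile the fixed LTE dose in Section 3.1.5 with the hold and dose-reduction provisions of Section 3.1.3.
- Optionally, add to Section 8.4.8 a descriptive breakdown of LTE response and safety by the dose received on Day 71, alongside the pooled table.

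The cost is amendment wording and matching SAP text. The optional breakdown needs one grouping variable; its drawback is small subgroups.

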5.1.1 Retesting During Screening or Lead-in Period

Retesting of laboratory parameters and/or other assessments within any single Screening or Lead-in period will be permitted (in addition to any parameters that require a confirmatory value).

Any new result will override the previous result (i.e., the most current result prior to Randomization) and is the value by which study inclusion will be assessed, as it represents the subject's most current, clinical state.

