3 INVESTIGATIONAL PLAN

3.1 Study Design and Duration

This is a Phase 1b/2, multicenter, open-label study to evaluate the safety, efficacy, dose response, and pharmacology (PK, target engagement and PD) of BMS-986004 in subjects with ITP.

The study will comprise a short-term period and a long term extension (LTE) period.

The short-term period, is divided into three phases: Response Phase (6 weeks), Remission Phase (6 weeks) and Follow Up phase (8 weeks).

Screening evaluations to determine subject eligibility will be performed 21 days prior to study drug administration. The screening period may exceed 21 days but not more than 42 days total, and only after a discussion with and approval by the Study Director. If an extension in screening time is granted, the patient must still follow the platelet count rules for enrollment. The baseline platelet count determining enrollment eligibility will be based on the mean of two determinations taken within a week of the first dose. To be eligible for enrollment, platelet count needs to be less than $30,000/\text{mm}^3$ and show stable or declining trend. If the mean platelet count is between $30,000 - 35,000/\text{mm}^3$ the subject may be considered for enrollment on a case by case basis after discussion with and approval by the Study Director.

Following screening, a total of 40 evaluable subjects are planned for the study. Subjects are considered evaluable if they receive the first 4 doses of study drug and complete the required

safety and efficacy evaluations at Day 50. Non-evaluable subjects will be replaced to maintain a count of 10 subjects in each dose panels, except subjects will not be replaced if they are discontinued from the study secondary to an adverse event unless the adverse event can be determined to be unrelated to treatment.

Subjects are treated in dose panels of 10 subjects each. Four (4) dose panels are planned to be enrolled sequentially in an ascending manner, with dose intensity selected to provide increased levels of immunosuppression at steady state. Dose levels (range from 75 mg to 1500 mg administered every two weeks) that are planned to be evaluated in this trial are expected to elicit a range of clinical response.

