3.3.1 Inclusion Criteria

1. Signed Written Informed Consent

- a) The signed written informed consent form must be obtained from the subject in accordance with requirement of the study center's IRB, prior to initiation of any protocol required procedures.

2. Target Population

- a) Adults (≥ 18 years old), diagnosed with persistent or chronic ITP according to American Society of Hematology (ASH)/British Committee for Standards in Haematology (BCSH) guidelines, with or without prior splenectomy.
- b) Subjects previously received one or more prior ITP therapies and must have had initially responded to at least one prior ITP therapy. Previous treatments for ITP include but are not limited to TPO mimetics/agonists, corticosteroids, immunoglobulins, azathioprine, danazol, cyclophosphamide and/or rituximab.
- c) Subjects have had relapsed ITP i.e. failed to achieve a sustained (for more than 3 month) platelet count $\geq 50,000/\text{mm}^3$ to at least one prior ITP therapy.
- d) The platelet count (calculated from the mean of the 2 counts taken within a week of the first dose, during the screening and pre-treatment periods) must be less than $30,000/\text{mm}^3$ with no count greater than $35,000/\text{mm}^3$. If the mean of the counts is between $30,000$ - $35,000/\text{mm}^3$, the subject may still be eligible but enrollment will be on a case by case basis and require approval by the Study Director.
- e) Subject Re-enrollment: This study permits the re-enrollment of a subject that has discontinued the study as a pre-treatment failure (ie, subject has not been randomized / has not been treated). If re-enrolled, the subject must be re-consented.
- f) A complete blood count must be within the reference range (including white blood count [WBC] differential not indicative of a disorder other than ITP), with the following exceptions:
 - i) subjects with hemoglobin levels between 9 g/dL for females and 10 g/dL for males and the lower limit of normal (LLN) are eligible for inclusion, if anemia was clearly attributable to ITP (excessive blood loss);
 - ii) absolute neutrophil count (ANC) greater than or equal to $1500/\mu\text{L}$ (elevated WBC/ANC due to corticosteroid treatment is acceptable)
- g) Prothrombin Time/International Normalized Ratio (PT/INR) and activated partial thromboplastin time (aPTT) must have been within 80% to 120% of the normal range with no known hypercoagulable state.

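### The screening retest rule in protocol Section 5.1.1 does not exempt platelet counts, so a repeat can erase a count above the 35,000/mm³ cap in inclusion criterion 2d

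*Protocol*

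**What the plan says.** Protocol Section 5.1.1 covers laboratory parameters and other assessments in general. Retesting within a screening period "will be permitted (in addition to any parameters that require a confirmatory value"), and then: "Any new result will override the previous result (i.e., the most current result prior to Randomization) and is the value by which study inclusion" is decided. It names no test, sets no maximum number of retests, and does not set platelet count apart. Platelet count is part of the screening laboratory tests in Table 5.1-1.

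Inclusion criterion 2d (Section 3.3.1) defines the qualifying platelet count as "calculated from the mean of the 2 counts taken within a week of the first dose, during the screening and pre-treatment periods". That mean must be below 30,000/mm³, and no count may exceed 35,000/mm³. For a mean of 30,000 to 35,000/mm³, "the subject may still be eligible but enrollment will be on a case by case basis and require approval by the Study Director".

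Section 3.1 repeats the averaging rule: "The baseline platelet count determining enrollment eligibility will be based on the mean of two determinations taken within a week of the first dose". It also asks for a stable or declining trend and adds: "If an extension in screening time is granted, the patient must still follow the platelet count rules for enrollment". Section 3.3 allows no exceptions to the entry criteria. The laboratory note in Table 5.1-1 judges eligibility against 2d on an average of three counts (screening, Day -1 and predose) instead of two.

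**The concern.** The two rules treat an earlier count in opposite ways. Under 2d every count matters: each enters the mean, and any one above 35,000/mm³ disqualifies. Under 5.1.1 an earlier result stops counting once a newer one exists. A cap on every count cannot be enforced if a repeat erases the count that broke it.

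Platelet counts vary from draw to draw, so repeating after a high value favours patients who happen to be low on the repeat. Someone whose usual count is about 36,000/mm³ already meets the 30,000/mm³ part of the response definition on a typical day; only the doubling and the absence of bleeding remain. There is no control arm to show how much of a later rise would have occurred anyway. Response rates feed the dose-prediction models (Section 8.5, Appendix 2), the six-responder trigger for a cohort below 75 mg (Section 3.1), and the monitoring committee's comparison with background rates (Section 7). In a cohort of 10, one patient moves the rate by 10 percentage points.

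**Working it through.** **Plan's own figure.** The plan gives none for the retest rule. Its only sample-size figure, a 90% interval of (0.15, 0.70) for 4 of 10, reproduces as an exact interval (0.150 to 0.696). Nothing below depends on it.

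**Worked example.** Counts of 24,000 then 44,000; repeat 26,000.

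- 2d as written: mean (24,000 + 44,000)/2 = 34,000, and 44,000 > 35,000. Fails the ordinary route on both tests. The mean lies in the Study Director band; the text does not say whether the cap still binds there.
- Repeat overrides the previous result (44,000): mean (24,000 + 26,000)/2 = 25,000, largest count 26,000. Passes outright, with no approval needed.
- Repeat added: mean (24,000 + 44,000 + 26,000)/3 = 31,333, largest count 44,000. Fails the ordinary route.

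**Simulation.**

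- From the documents: thresholds of 30,000 (mean) and 35,000 (cap).
- Assumed: independent lognormal counts around a stable true mean of 36,000; within-patient CV 20%, 30%, 40%; one retest, taken only after failing 2d; Study Director route left out.
- Counts are exp(μ + σZ), with σ² = ln(1 + CV²), μ = ln(36,000) − σ²/2, and 400,000 patients per setting.
- With first count a, second b and retest r, admission means:
  - 2d, no retest: (a+b)/2 < 30,000 and max(a,b) ≤ 35,000.
  - Later count replaced: 2d passes, or the pair (a, r) meets both tests.
  - Higher count replaced: 2d passes, or the pair (min(a,b), r) meets both tests.
  - Repeat added: 2d passes, or (a+b+r)/3 < 30,000 and max(a,b,r) ≤ 35,000.

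| Admitted, true mean 36,000 | CV 20% | CV 30% | CV 40% |
|---|---|---|---|
| 2d, no retest | 10% | 19% | 25% |
| Retest replaces later count | 17% | 30% | 38% |
| Retest replaces higher count | 23% | 40% | 49% |
| Retest added, cap on all | 11% | 21% | 26% |

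Ratios to 2d: later count replaced, 17/10 = 1.7, 30/19 = 1.6, 38/25 = 1.5; higher count replaced, 23/10 = 2.3, 40/19 = 2.1, 49/25 = 2.0.

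**No-drug response.** With the qualifying mean as baseline, the proportion meeting the platelet part of R at any of the seven Response Phase visits with no drug effect is about 9/42/66% for patients admitted only through substitution of the later count, and 9/43/67% for those admitted by 2d. There is no excess per patient.

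**The case against.** The strongest reply is that the specific criterion governs the general one. Averaging is stated in the synopsis, Section 3.1, criterion 2d and Table 5.1-1; a stable or declining trend cannot be shown with one count; and Section 3.3 allows no exceptions. Section 5.1.1 replaces one result and abolishes neither the mean nor the cap. Its parenthesis on confirmatory values can be read as setting multi-value parameters apart.

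Much of this stands. A reader might infer that 5.1.1 cancels 2d, so that one low repeat admits a patient. The documents do not say that. Take 38,000 and 33,000 with a repeat of 28,000. Replacing the 33,000 leaves 38,000 above the cap and a mean of 33,000. Replacing the 38,000 leaves a mean of 30,500, which is not below 30,000. Neither passes outright. The larger admission figures of 29/45/54% arise only if the newest count alone decides.

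A reader might also infer that retest admissions respond more often without drug. On the newest-count-alone reading the simulation gives about 17/53/73% against 9/43/67%. The gap disappears if a separate Day 1 count is the baseline (4/20/35% by both routes), as the protocol's references to a Day 1 baseline suggest. It would not necessarily disappear if the Day 1 count were itself the qualifying repeat.

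The Study Director route also matters. If every mean in the 30,000–35,000 band were approved with the cap kept, 23/27/30% would be admissible with no retest, so part of the increase concerns patients the plan already contemplates, though only with approval.

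What the reply leaves unanswered is which counts enter 2d after a repeat. Requiring 2d to be met does not settle that, and the only text that addresses it is the override. The parenthesis does not say that earlier values stand.

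**Conclusion.** The concern holds in limited form. Followed as written, 5.1.1 lets a platelet repeat displace a count above 35,000/mm³ that 2d says must count, with no limit on repeats. The two-count mean survives; the protection given by the cap does not.

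With one substituting retest, about 1.5 to 1.7 times as many patients with a true mean of 36,000/mm³ are admitted if the later count is replaced, and about 2.0 to 2.3 times if the higher is. This rests on assumed CVs, independent counts, one retest and no Study Director route. It shows direction and range only; further retests would enlarge the effect. The documents do not show how many screened patients lie near this level, so no number of affected subjects can be given.

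The consequence is more above-threshold patients in small uncontrolled cohorts, not a higher no-drug response rate per admitted patient. Safety is the primary objective and there is no formal hypothesis, so this should be corrected but does not undermine the trial.

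Two related loose ends belong with it. The two-count rule and the three-count average in Table 5.1-1 disagree, which leaves a site unsure where a repeat goes. The override is also timed to randomization, an event this trial does not have.

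**What to change.** - In Section 5.1.1, exempt the criterion 2d platelet counts from the override.
- In 2d, state that a repeat is added to the earlier valid counts in the qualifying week and never substituted, except for a documented sample error, and that the 35,000/mm³ check covers every such count.
- Reconcile the two-count mean (synopsis, Section 3.1, criterion 2d) with the three-count average in Table 5.1-1.
- In Section 5.1.1, replace the reference to randomization with first dose.

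The cost is a few sentences in 5.1.1 and 2d, one corrected table note, and a few more screen failures.
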